- 1) To compare adherence among persons across the three study arms.
- 2) To evaluate the safety, tolerability and acceptability of treatment in the three arms.

3. Background

Globally, an estimated 70 – 80 million persons are chronically infected with hepatitis C (HCV). Chronic hepatitis C is associated with long-term complications including liver cirrhosis, hepatocellular carcinoma and end-stage liver disease. Chronic hepatitis C is treatable and treatment can cure infection such that HCV RNA is undetectable and persons cannot transmit virus and risk for chronic complications decreases substantially. Treatment access has been hampered in much of the world in part due to the low efficacy and toxicity of the previous generation of regimens. The landscape of HCV treatment has changed dramatically over the past few years with the FDA approval of highly efficacious, non-toxic second generation direct acting antiviral agents. With these advances in treatment, questions have arisen about delivery of these agents among populations in resource-limited settings (RLS) given some of the inherent differences in HCV infected patients in these settings. Ideally, a treatment regimen for RLS should be pan-genotypic; thereby, not requiring HCV genotype testing which can be cost prohibitive and rarely available in these settings. Moreover, treatment delivery strategies need to optimize adherence particularly in populations that have had suboptimal adherence such as people who inject drugs (PWID).

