Accordingly, we propose to conduct a pilot trial among people who inject drugs in India that evaluates the efficacy of a shortened 4-week regimen including pegylated interferon and two DAAs to an all-oral 12-week pan-genotypic regimen with both delivered using DOT and a third arm which will comprise SOF/DAC delivered as per standard of care. Further, we will also estimate cost per SVR in each of these three arms as costs associated with DOT could potentially offset the benefit. These data will provide critical insight into the optimal delivery strategy for people who use drugs in resource limited settings.

4. Study Procedures

a. Study design, including the sequence and timing of study procedures

This will be a non-blinded randomized clinical trial with 150 participants randomized at a 1:1:1 allocation ratio to one of three treatment arms.

Arm 1: Sofosbuvir (400mg/daily) + Daclatasvir (60mg/daily) + Pegylated Interferon alfa-2a (180µg/weekly) for 4 weeks with a field-based DOT approach

Arm 2: Sofosbuvir (400mg/daily) + Daclatasvir (60mg/daily) for 12 weeks with a field-based DOT approach

Arm 3: Sofosbuvir (400mg/daily) + Daclatasvir (60mg/daily) for 12 weeks with standard of care dispensation (4 monthly doses)

Pegylated-interferon alfa-2a (PEG) will be delivered subcutaneously once weekly. Sofosbuvir (SOF) and Daclatasvir (DAC) will be taken orally once daily for the entire study period.

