Vital signs: Assessment of vital signs will include measurement of resting blood pressure, pulse, respiratory rate and temperature.

Pregnancy testing: All females of childbearing potential will have a urine pregnancy test at the Screening and Baseline visits.

Survey: We will use the EuroQOL-5D as well as the WPAI: Hepatitis C Quality of Life Surveys. These will be translated into the local language. While these surveys are intended to be self-administered, low literacy rates in our population will require that they be interviewer administered. We will also include brief questions on frequency of drug and alcohol use.

Chart Review: The YRG-JHU ICC maintains an electronic database to monitor client visits, test results and service utilization. Data that are available through this database will be abstracted from these patient records rather than collected de novo. Specifically, we are interested in HIV status and whether participants are engaged in antiretroviral therapy and/or opioid substitution therapy.

b. Study duration and number of study visits required of research participants.

Participants in all Arms will have 4 study visits (Screening, Baseline, End of Treatment and SVR12). Participants in Arm 1 will have an additional 3 visits for interferon injections, and participants in Arm 3 will have an additional two visits to pick up medication refills. The duration of the study will be 16 weeks for Arm 1 and 24 weeks for Arms 2 and 3.

c. Blinding, including justification for blinding or not blinding the trial, if applicable.

This study will not be blinded. In part, this is so that clinicians can appropriately monitor for side effects associated with pegylated interferon alfa-2a. The regimens delivered require different forms of delivery (e.g., pegylated interferon is an injectable medicine) and for different durations of time making blinding not feasible.

d. Justification of why participants will not receive routine care or will have current therapy stopped.

All participants will be able to receive the same routine medical care that they receive at the center and no other therapies will be stopped.

e. Justification for inclusion of a placebo or non-treatment group.

This study does not involve a placebo group.

f. Definition of treatment failure or participant removal criteria.

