Peglyated-interferon alfa-2a is commercially available as Taspiance by Emcure Pharmaceuticals in India and will be provided in this study as 180 µg/0.5 mL pre-filled syringes. Each syringe is to deliver 0.5 mL of drug product. The formulation, which is subcutaneously administered, contains sodium chloride, polysorbate 80, benzyl alcohol, sodium acetate trihydrate, acetic acid, and water for injection. The solution is colorless to light yellow and the pH is 6.0 ± 0.5.

Packaging and Labeling

The PEG will meet all applicable requirements of Good Manufacturing Practices: Manufacture of

investigational medicinal products (July 2003) and the Drug Controller General India (DCGI).

Storage and Handling

Peglyated-interferon alfa-2a prefilled syringes will be stored in the refrigerator at 2 °C to 8 °C (36 °F to 46 °F) protected from light and will not be frozen or shaken. Syringes are for single use only.

b. Justification and safety information if FDA approved drugs will be administered for non-FDA approved indications or if doses or routes of administration or participant populations are changed.

N/A

c. Justification and safety information if non-FDA approved drugs without an IND will be administered.

N/A

7. Study Statistics

a. Primary outcome variable.

The primary outcome will be sustained virologic response (SVR12), which is defined as HCV RNA < lower limit of quantification 12 weeks after treatment completion.

b. Secondary outcome variables.

Adherence for comparison across the three arms will be defined using a combination of the biometric data for Arms 1 and 2 and self-report and pill counts for Arm 3. Serious adverse events requiring dose modification or treatment discontinuation will include primarily laboratory abnormalities including anemia, neutropenia and thrombocytopenia. For any adverse event outcome, we will consider occurrence of any of the side effects commonly associated with treatment with pegylated interferon alfa-2a, including but not limited to fatigue, headache, pyrexia, myalgia, rigors, insomnia, nausea, alopecia, irritability, arthralgia, anorexia, dermatitis, depression, or fatigue.

c. Statistical plan including sample size justification and interim data analysis.

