All analyses will be conducted as intention to treat. We will use a chi-squared test of proportions to compare the proportions that achieve SVR12. Pairwise comparisons with correction for multiple comparisons will be conducted to directly compare Arms 1 and 2, Arms 1 and 3 and Arms 2 and 3. For secondary outcomes, chi squared tests of proportions will be used to compare categorical outcomes and a Wilcoxon rank-sum test will be used to compare adherence.

The primary objective of this study is to test the feasibility of DOT for HCV treatment among HCV-infected persons with substance use history in a resource limited setting. An additional objective is to generate pilot data to plan a larger powered study. We hypothesize that SVR12 will be higher in Arm 1 compared to Arms 2 and 3. Assuming a two-sided $\alpha=0.05$, 50 people in each arm and 70% achieving SVR12 in Arm 3, we will have >80% power to detect a difference of 25% (e.g., 95% completion in the SOF+DAC+PEG).

No interim analyses will be conducted as with 150 participants, it will not be possible to observe statistical differences prior to the completion of the trial.

d. Early stopping rules.

As we do not plan to do interim analyses, the only reason for stopping the trial would be a higher frequency than expected of serious adverse events. We will continually monitor the frequency of serious adverse events and if this frequency is 10% or higher, we will prematurely stop the trial.

8. Risks

a. Medical risks, listing all procedures, their major and minor risks and expected frequency.

It is anticipated that most participants who complete their full course of treatment with optimal adherence will clear hepatitis C from their bodies. However, for those individuals who do not respond to treatment, it is possible that non-response will affect their ability to respond to other drugs for hepatitis C in the future. However, with the newer direct acting antiviral (DAA) regimens, response rates have been demonstrated to be comparable in treatment naïve and prior non-responders. The primary risk related to taking these medications is with respect to side effects associated with pegylated interferon alfa2a.

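### Intention to treat governs the safety outcomes and no dosed population is defined, so Arm 1 adverse event rates could be understated, probably slightly

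*Combined protocol and SAP*

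**What the plan says.** Section 7c opens its analysis plan with "All analyses will be conducted as intention to treat". Nothing there or elsewhere restricts the rule to efficacy, and no safety, as-treated or at-least-one-dose set is defined.

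Safety is a stated aim. Secondary objective 2 in section 2 is "To evaluate the safety, tolerability and acceptability of treatment in the three arms". Section 7b defines the outcome: "For any adverse event outcome, we will consider occurrence of any of the side effects commonly associated with treatment with pegylated interferon alfa-2a", followed by an open list that includes fatigue, headache, insomnia and nausea. Section 7c gives the test: "For secondary outcomes, chi squared tests of proportions will be used to compare categorical outcomes".

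The design in section 4a is "150 participants randomized at a 1:1:1 allocation ratio to one of three treatment arms", so 50 per arm. Section 4c adds "This study will not be blinded". Only Arm 1 involves injections.

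**The concern.** Intention to treat is the natural choice for SVR12, where counting non-starters is usually conservative. For harms it works the other way: a participant never exposed to PEG brings the Arm 1 rate closer to that of the arms without it. The protocol identifies PEG side effects as the main risk of treatment (section 8a) and argues that four weeks of PEG should cause few of them (section 6a). A rule that can only narrow the observed safety contrast leans towards that expectation.

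There are routes to an undosed Arm 1 participant. Allocation is known when the envelope is opened, and a participant may stop for any reason (section 4a5.4). Two checks are also worded as specific to Arm 1: PEG hypersensitivity (exclusion criterion 8) and the retinal examination (section 4a5.6). Sections 5 and 4a3 instead place PEG eligibility and the retinal examination before randomization. If either check were applied after allocation, an Arm 1 participant without PEG could result.

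**Working it through.** **The plan's own figure.** The only power statement in section 7c concerns SVR12: "50 people in each arm and 70% achieving SVR12 in Arm 3", against 95%, at two-sided alpha 0.05, claimed as above 80%. The normal approximation gives 92.0% and exact enumeration of the chi-squared test 94.8%. The claim reproduces, but it says nothing about safety.

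**How likely is non-start?**
- Section 4a5.1 lists procedures to be completed before randomization and dosing, so both belong to the Baseline/Day 1 visit.
- PEG is given weekly for four weeks (section 4a5.2), yet Arm 1 has only 3 visits beyond the four common ones (sections 4a2 and 4b).
- Section 10 pays Arm 1 INR 1500 = 4 × 300 + 3 × 100, which matches three separate injection visits.
- The natural inference, not stated outright, is that the first injection is given at Day 1, soon after allocation. The number never dosed may then be zero or one.

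**Inputs for the size.** From the documents: 50 per arm, two-sided alpha 0.05 (stated for SVR12 and carried over here), chi-squared test. Assumed, because the documents give no value: adverse event rate p = 60% with interferon and b = 30% without; k Arm 1 participants never given PEG; a comparator arm of 50, all dosed, at 30%.

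**Formulas for the intention-to-treat rate in Arm 1.**
- Never-starters observed, with the background rate: [p(50 − k) + bk]/50. Each lowers the rate by (0.60 − 0.30)/50 = 0.6 percentage points.
- Never-starters counted as event-free: p(50 − k)/50. Each lowers it by 0.60/50 = 1.2 percentage points.

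For k = 5: (0.60 × 45 + 0.30 × 5)/50 = 28.5/50 = 57.0%, and 0.60 × 45/50 = 54.0%.

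Power is by exact enumeration of the uncorrected chi-squared test. The dosed-only analysis compares 50 − k at 60% with 50 at 30%.

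| k of 50 | Rate, background | Power | Rate, event-free | Power | Power, dosed only |
|---|---|---|---|---|---|
| 0 | 60.0% | 88% | 60.0% | 88% | 88% |
| 1 | 59.4% | 86% | 58.8% | 85% | 85% |
| 2 | 58.8% | 85% | 57.6% | 82% | 87% |
| 3 | 58.2% | 83% | 56.4% | 78% | 84% |
| 5 | 57.0% | 80% | 54.0% | 70% | 84% |

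The dosed-only column is not monotone because the exact test is discrete. With one never-starter, the dosed-only analysis has no power advantage.

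**Which column applies?** The outcome covers common symptoms and is not limited to events attributed to PEG, so an undosed participant who is followed can have one; that favours the background column. But section 8b finds side effects through weekly Arm 1 visits and daily field visits. Someone who declines everything may not be observed and could be recorded as event-free. The two columns bracket the answer.

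**The case against.** The strongest reply is that the design almost removes the premise. Consent covers all three arms and is allotted 1 to 1.5 hours (section 4a3), everyone must be eligible for PEG (section 5), and the first injection appears to follow allocation at the same visit. No section expects or describes an Arm 1 participant who never receives PEG. This stands, and it is why the expected effect is small. The 12% who did not complete treatment in the earlier pilot are no guide, since the documents do not say that any of them never started.

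Second, harm by assigned strategy is a valid randomized comparison in a trial of regimens and delivery modes. This also stands: it is a reason to keep the intention-to-treat safety table, but not a reason to have no dosed analysis.

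Third, participants who start PEG and then stop or have it reduced are in both sets, so a dosed set leaves their handling unchanged. That is correct.

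Fourth, section 8c1.1 already records relatedness, severity and action taken for each event, so never-dosed participants could be reported without changing the plan. They could, but the denominator would then be chosen after the data are seen, in an open-label trial.

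A reader might infer that PEG harm will be understated, or that each never-starter removes a full 1/50 of the Arm 1 risk. The documents support neither. The first needs never-starters, whom they do not establish. The second holds only if the undosed are counted as event-free; at the assumed 30% background the loss is half that.

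**Conclusion.** The gap is real and minor. The intention-to-treat rule is unrestricted, adverse events fall under it, and no dosed population exists. If any Arm 1 participant never receives PEG, the Arm 1 rate is diluted towards the other arms, assuming that PEG raises the event rate.

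The size depends on quantities the documents do not give. With no never-starters the two analyses coincide. On the assumed 60% and 30%, the loss is 0.6 to 1.2 percentage points per never-starter. Even at 5 of 50, which the schedule makes unlikely, the 30-point contrast shrinks to 27 or 24 points. The documents do not support a claim that the safety conclusion is biased in practice, nor one that intention to treat is wrong for safety. They support adding a second, pre-specified analysis.

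**What to change.** In section 7c:
- Keep intention to treat for SVR12 and for the other efficacy and adherence comparisons.
- For the section 7b safety outcomes, pre-specify an analysis of participants who received at least one dose of study drug, grouped by regimen received, with Arm 1 meaning at least one PEG injection. Present it beside the intention-to-treat safety table, not in place of it.
- Report by arm the number randomized but never dosed, and the number in Arm 1 who took oral drug only.

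Most of the data are already planned: fingerprint-logged deliveries in Arms 1 and 2, injections given in clinic, and dispensing in Arm 3. Because Arm 3 doses are not observed, the text should say whether dispensing alone counts as a dose or whether self-report or pill count is also needed.

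The cost is a sentence or two in the plan and one extra table. The dosed groups may be slightly smaller than 50 and are not strictly as randomized, which is why the intention-to-treat table stays. No dose or clinical rule changes.

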Subjects in Arm 1 will be required to visit the Bilaspur ICC once weekly for four weeks. During these visits, participants in Arm 1 will receive their pegylated interferon alfa-2a shots subcutaneously at the clinic by a registered medical practitioner. They will be compensated INR 100 (USD 1.5) for these visits (since this is not the standard of care).

Subjects in Arms 1 and 2 will also receive 3 doses of SOF and DAC, which they will be instructed to take home and use as backup in case there is a problem receiving the daily medication from field workers. Otherwise, all doses of SOF and DAC will be delivered as directly observed therapy (DOT) daily in the field including Saturday and Sunday doses. Peer-health workers (PHW) (1 per 15-20 participants: total 4 for the study) will deliver the SOF and DAC via DOT on a daily basis to a location of the participant's choosing. We will provide the PHW with laptops/tablets that have a fingerprint reader to record the daily delivery of SOF and DAC and also to also ensure that the drugs are being delivered to the correct participant.

Subjects in Arm 3 will receive their first 4 weeks of treatment supply at baseline and two refills of 28 day's worth of doses at Weeks 4 and 8.

Dose Reduction

If a serious adverse reaction develops in Arm 1 participants during the course of treatment (See Section 8c), the dose of PEG will be modified according to standard guidelines until the AE abates or decreases in severity. See Table 1 for procedures related to depression and see Table 2 for procedures related to hematologic abnormalities. Selective serotonin reuptake inhibitors are available through government hospitals in India and will be made available to study subjects as needed. If persistent or recurrent serious adverse events develop despite adequate dosage adjustment, treatment will be discontinued.

Table 1. Procedures for Dose modification for serious adverse events related to depression

Depression Severity	Initial Management (4-8 weeks)		Depression		
	Dose modification	Visit Schedule	Remains stable	Improves	Worsens
Mild	No change	Evaluate once weekly by clinician at visit and daily recording of symptoms by outreach worker in field	Continue weekly visit schedule	Continue weekly visit schedule	(See moderate or severe depression)

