It is anticipated that the majority of side effects will be related to pegylated interferon as side effects associated with SOF and DAC are rare. With pegylated interferon, the side effects most commonly reported that are of concern include depression, suicidal thoughts, relapse of drug use by former drug users and bacterial infections complicated or made possible by low white blood cell counts. Notably, previously pegylated interferon has primarily been used as part of 48-week regimens and the majority of the side effects occurred beyond 20-24 weeks of therapy, so we anticipate that the frequency of side effects in our study participants will be lower than what has been observed with longer regimens.

Because we will be delivering daily doses of SOF and DAC for Arm 1 and 2 participants in the field, there are additional risks related to disclosure of a participants' HCV status through the receipt of this medication every day from a field worker.

b. Steps taken to minimize the risks.

Procedures to minimize risk include carefully training personnel 1) to be competent in venipuncture; 2) to recognize and address psychological issues; and 3) to maintain confidentiality. Psychological risks are minimized by the availability of trained counselors in the study clinic. If further assistance is needed, we will have access to the psychiatry department at CIMS. The study clinicians are also trained in CPR as part of medical education in India. Abnormal clinical findings and/or laboratory values will be conveyed in a timely manner to the participants and, with the consent of the subject, form the basis of a facilitated referral to a hospital, clinic, or a physician of the subject's choosing. Subjects who continue to report active drug and alcohol use will be offered individual counseling and referral for treatment of their drug use or alcohol use, should they request one. All participants will receive risk reduction counseling (including the importance of abstaining from alcohol use) at each visit after data collection is completed and prior to scheduling subsequent study visits. This intervention will make our cohort somewhat different from the general population of PWID, but it is useful to provide lower bounds of counseling. We have established cooperation with several drug abuse treatment organizations and this may help facilitate personalized facilitated referrals.

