All AEs will be assessed by the principal investigator or qualified designee (Study Doctor) and recorded on the AE form. The AE entry will indicate whether or not the AE was serious, the start date (AE onset), the stop date (date of AE resolution), whether or not the AE was related to study drug or a study procedure, the action taken with the study drug due to the AE and the severity of the AE. The principal investigator will be responsible for final review and confirmation of accuracy of events, relationship and severity confirmed by signature on the AE form.

The relationship to the study drug will be assessed using a combination of clinical judgement and the following considerations:

- NO: Evidence exists that the adverse event has an etiology other than the study drug. For serious adverse events, an alternative causality will be provided (e.g., pre-existing condition, underlying disease, intercurrent illness or concomitant medication).
- YES: There is a reasonable possibility that the event must have been caused by the investigational medicinal product.

It should be emphasized that ineffective treatment should not be considered as causally related in the context of AE reporting.

The relationship to study procedures (e.g., invasive procedures such as venipuncture or biopsy) should be assessed using the following considerations:

- NO: Evidence exists that the AE has an etiology other than the study procedure.
- YES: The AE occurred as a result of protocol-mandated procedures such as venipuncture.

The severity grading of AEs will be assessed as Grade 1, 2, 3 or 4 using a standard grading scale for severity of adverse events and laboratory abnormalities. This has been adapted from those used for Industry sponsored trials in the US. For AEs associated with laboratory abnormalities, the event should be graded on the basis of the clinical severity in the context of the underlying conditions; this may or may not be in agreement with the grading of the laboratory abnormality.

8c2. Serious Adverse Events

A **serious adverse event (SAE)** is defined as follows:

Any adverse drug experience occurring at any dose that results in any of the following outcomes:

- Death
- Life-threatening situation (subject is at **immediate** risk of death)
- In-patient hospitalization or prolongation of existing hospitalization (excluding those for study therapy or placement of an indwelling catheter, unless associated with other SAEs)

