- Persistent or significant disability/incapacity
- Congenital anomaly/birth defect in the offspring of a subject who received investigational medicinal product
- Other medically significant events that may not be immediately life-threatening or result in death or hospitalization, but based upon appropriate medical and scientific judgement, may jeopardize the subject or may require medical or surgical intervention to prevent one of the outcomes listed above

Examples of such events are as follows:

- Intensive treatment in an emergency room or at home for an allergic bronchospasm
- Blood dyscrasias or convulsions that do not result in hospitalization
- Development of drug dependency or drug abuse

8c2.1. Classification of Serious Adverse Events (SAEs)

- Death is an outcome of an AE, and not an adverse event in itself. In reports of death due to “Disease Progression,” where no other information is provided, the death will be assumed to have resulted from progression of the disease being treated with the study drug.
- The subject may not have been on the study drug at the occurrence of the event. Dosing may have been given as treatment cycles or interrupted temporarily before the onset of the SAE, but may have contributed to the event.
- “Life-threatening” means that the subject was at immediate risk of death from the event as it occurred. This does not include an event that might have led to death if it had occurred with greater severity.
- Complications that occur during hospitalizations are AEs. If a complication prolongs the hospitalization, it is an SAE.
- “In-patient hospitalization” means the subject has been formally admitted to a hospital for medical reasons, for any length of time. This may or may not be overnight. It does not include presentation and care within an emergency department.
- The investigator should attempt to establish a diagnosis of the event on the basis of signs, symptoms and/or other clinical information. In such cases, the diagnosis should be documented as the AE and/or SAE and not the individual signs/symptoms.

A distinction should be drawn between the seriousness and the severity of the AEs. An AE that is assessed as Grade 4 (potentially life-threatening) should not be confused with an SAE. Severity is a category utilized for rating the intensity of an event; and both AEs and SAEs can be assessed as Grade 4. An event is defined as “serious” when it meets one of the predefined outcomes described above.

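### The only trial-stopping rule, an SAE frequency of 10% or higher, has no denominator, unit, minimum number or arm scope: one early SAE can trip it, and pooling hides an Arm 1 excess

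*Combined protocol and SAP*

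**What the plan says.** Section 7c plans no interim analysis. Section 7d then states that "the only reason for stopping the trial would be a higher frequency than expected of serious adverse events", and gives the rule: "We will continually monitor the frequency of serious adverse events and if this frequency is 10% or higher, we will prematurely stop the trial". The wording is mandatory, with no review step between reaching 10% and stopping. It names no arm and speaks of stopping the trial, so the natural reading is trial-wide.

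The visible text nowhere gives a denominator (screened, randomised, treated or planned), a unit (SAE events or participants with an SAE), a minimum number, or the expected frequency that 7d mentions. Section 8c2 defines an SAE by outcome and 8c2.1 sets reporting, but neither is tied to the 10%.

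On where harm is expected, Section 8a says: "It is anticipated that the majority of side effects will be related to pegylated interferon as side effects associated with SOF and DAC are rare". Only Arm 1 receives pegylated interferon (PEG; Section 4a). Sections 3 and 6a report no SAEs in the PEG arm of the earlier pilot.

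**The concern.** A proportion checked continually is unstable while its denominator is small. With no minimum number, a single event can meet a 10% limit very early, even when the true rate is far below 10%. The trial could then end by chance.

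The opposite problem arises from pooling. If the excess lies in one of three equal arms, the other two pull the overall rate down, and the limit may not be reached although Arm 1 is well above 10%.

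Both problems follow from what 7d leaves open. Staff applying it in good faith could reach different decisions on the same data, and in an open-label trial they would be choosing the interpretation after seeing the events.

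**Working it through.** **Inputs from the documents.** 150 participants allocated 1:1:1, so 50 per arm (Sections 4a and 7c); limit 10% or higher, monitored continually (7d). The plan states no error rate or derivation for the limit, so there is no figure to reproduce.

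**Assumptions.** True SAE rates are not given, so a range is used. Participants with an SAE are counted over participants started. Enrolment pace and reporting delay are not given either. Delay is expressed as the number L of further participants who have started before an SAE is known.

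**Step 1: smallest trigger.** k SAEs among n participants reach the limit when k/n ≥ 0.10, that is n ≤ 10k. One SAE suffices up to n = 10, and two up to n = 20. The chance of at least one SAE in the first 10 is 1 − (1 − p)^10 = 9.6, 18.3, 26.3 and 40.1% for p = 1, 2, 3 and 5%.

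**Step 2: chance of ever stopping, running trial-wide proportion.** Exact recursion on the cumulative count over 150 participants, same true rate in all arms. The SAE of participant i enters when participant i + L has started, with the denominator capped at 150.

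| Delay L | p = 1% | 2% | 3% | 5% |
|---|---|---|---|---|
| 0 | 10.0% | 20.0% | 30.0% | 50.0% |
| 5 | 5.4% | 11.5% | 18.5% | 35.4% |
| 10 | 0.5% | 2.1% | 5.1% | 16.5% |
| 20 | 0.02% | 0.15% | 0.6% | 4.7% |

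**Step 3: fixed pooled count.** 0.10 × 150 = 15. P(Bin(150, 0.05) ≥ 15) = 0.85%. At a true 5%, the same sentence thus gives a chance of stopping between 0.85% (fixed count) and 50% (running, no delay). At a true 15% in all arms the readings agree: 97.2% fixed and 99.6% running with no delay.

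**Step 4: dilution.** Arms 2 and 3 at 2%, Arm 1 at p1. The pooled rate is (p1 + 2 × 0.02)/3. The fixed count uses the exact sum of Bin(50, p1) and Bin(100, 0.02). The running rule is simulated with random blocks of 3, 6 and 9 as in Section 4a4. The last row is P(Bin(50, p1) ≥ 5), since 0.10 × 50 = 5.

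| | p1 = 15% | 20% | 25% |
|---|---|---|---|
| Pooled true rate | 6.3% | 8.0% | 9.7% |
| Fixed 15 of 150 reached | 5% | 21% | 49% |
| Running trial-wide, L = 0 | about 64% | about 78% | about 90% |
| Running trial-wide, L = 10 | about 28% | about 49% | about 71% |
| 5 of 50 within Arm 1 | 89% | 98% | 99.8% |

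With Arms 2 and 3 at 1%, the fixed pooled count is reached in 2, 12 and 37% of trials; at 3%, in 10, 32 and 60%.

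**Step 5: per-arm reading.** This removes dilution but not the small-denominator problem. A running proportion within one arm of 50 at a true 5% reaches 10% at some point with probability 48.9% if there is no delay.

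**The case against.** The strongest reply is that chance stops are unlikely in practice. The 10 to 50% figures need every SAE to be known as soon as a participant starts. Section 4a5.2 plans four peer workers with 15 to 20 participants each, so 60 to 80 may be under treatment together, and follow-up runs 16 to 24 weeks (Section 4b). A long delay relative to enrolment is plausible. The documents also point to low SAE rates: none in the earlier PEG arm, and side effects of the oral drugs described as rare. At 1 to 2%, the risk is 0.5 to 2.1% at a delay of 10 and nearly nil at 20. This stands, and the chance-stop figure should be quoted only as a delay-dependent range. But longer delay also weakens the running rule's ability to detect an Arm 1 excess (Step 4), so it does not rescue the rule.

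A second reply is that other safeguards exist: PEG modification and discontinuation rules (Section 4a5.2), weekly and daily monitoring (8b), and SAE reports to two IRBs within 24 hours (8c2.1). This also stands. A reader might infer that an Arm 1 excess would go unseen; the documents do not support that. What is missing is a usable criterion for stopping the trial.

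A reader might also infer that the SAE definition itself is in conflict, because Table 1 is titled "Procedures for Dose modification for serious adverse events related to depression" yet has a row for mild depression, or because 7b says "Serious adverse events requiring dose modification or treatment discontinuation will include primarily laboratory abnormalities including anemia, neutropenia and thrombocytopenia". That is not part of this point. Section 8c2 defines the term, 7d uses it, 7b can be read as describing a subset, and Table 1 concerns individual PEG management.

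Finally, a reader might pair each weakness with a single reading: early stops with a running proportion, dilution with a fixed count. The arithmetic does not bear this out, because a running pooled proportion dilutes too.

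**Conclusion.** The point holds. Section 7d cannot be applied reproducibly as written, and its natural trial-wide reading behaves poorly in two ways. A running proportion can be tripped by one SAE among the first 10 participants; how likely that is depends on the true rate and on reporting delay, neither of which the documents give. Any pooled version is insensitive to an excess confined to Arm 1: with Arm 1 at 20% and the others at 2%, it is flagged in 21% of trials by the fixed count and in about 49 to 78% by the running rule at delays of 10 to 0, against 98% for the same 10% applied within Arm 1 at full enrolment. A per-arm reading is also possible, and the text does not say which applies.

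All SAE rates are assumptions. A running-rule stop when Arm 1 is truly high is the right outcome and is not counted as a fault. A reader might infer that the efficacy conclusions are compromised; they are not, since the primary endpoint, test and sample size do not depend on this rule.

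**What to change.** In Section 7d:

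- Count participants with at least one SAE as defined in 8c2, over participants who have started treatment.
- Apply the count in Arm 1 (or in each arm) as well as overall.
- State a minimum number of participants before the proportion applies, or use a boundary that allows for chance. Have SAEs before that point prompt case review.
- Say whether the arm or the trial stops.
- Report the resulting stopping probabilities over a range of true rates and reporting delays.

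The threshold, minimum number and boundary are for the sponsor to choose.

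The cost is one paragraph and a short table. Two downsides should be disclosed. A minimum number or chance allowance reacts later to a true early excess. Counting by arm also raises the chance of a trigger when no arm is elevated: at a true 5% everywhere, 5 of 50 is reached in Arm 1 in 10.4% of trials and in at least one of three arms in 1 − (1 − 0.1036)^3 = 28.0%, against 0.85% for the pooled 15 of 150. Individual PEG rules, monitoring and SAE reporting need no change.
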